8.4.3.1. Primary Efficacy Analysis

- Percent of patients with complete resolution of both infantile spasms and hypsarrhythmia at Day 15 (complete response) will be compared between vigabatrin plus placebo and vigabatrin plus CBD 40 mg/kg/day groups using a chi square test.

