3.2.1. Inclusion Criteria

All patients must satisfy the following criteria to be considered for study participation:

1. Parent(s)/caregiver(s) fully comprehend and sign the informed consent form, understand all study procedures, and can communicate satisfactorily with the investigator and study coordinator, in accordance with applicable laws, regulations, and local requirements.
2. Male or female between 1 months to 24 months of age (inclusive) at time of consent.
3. Clinical diagnosis of infantile spasms, confirmed by video-EEG analysis (including at least one cluster of electroclinical spasms [≥ 3 in any 10-minute epoch]) and hypsarrhythmia) obtained during the Screening Period and read by a central reader.
4. General good health (defined as the absence of any clinically relevant abnormalities as determined by the investigator) based on physical and neurological examinations, medical history and clinical laboratory values completed during the Screening Visit (Visit 1).
5. In the opinion of the investigator, the parent(s)/caregiver(s) is (are) willing and able to comply with the study procedures and visit schedules.

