8.2. Sample Size Determination

A total of 190 patients (130 and 60 patients in the two groups) will provide 80% power with a two-sided alpha of 0.05 to detect a difference in response rate, assuming the response with vigabatrin alone is 40% and the response with vigabatrin with Cannabidiol Oral Solution is 60%.

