8.4.3. Efficacy Analyses

A 9-hour video EEG will be conducted during the Screening Period (Baseline) and a 24-hour video EEG will be conducted from Day 14 to Day 15 of the Initial Treatment Period. In addition, to confirm parent/caregiver report of relapse or complete resolution a 9-hour video EEG will be conducted during the Extended Treatment Period. For each video EEG, the number of spasms will be counted and the presence of hypsarrhythmia determined. Change from Baseline for each measure will be summarized by the median difference. Patients will be defined as having Complete Response, Partial Response, or Non-Response on Day 15 as defined in [Table 2](#), the percentage of patients who achieve a Complete Response and Partial Responders in each treatment arm will be compared using a chi-square test.

The results of the CGI-I assessments will be listed and summarized by descriptive statistics as appropriate. The responses to the seizure diary will also be summarized by dose level and scheduled time point. All efficacy summaries will be based on the ITT Population.

Details of these summaries will be provided in the SAP. For all inferential statistical tests, a 2-sided type I error rate of 0.05 will be used throughout.

For the secondary efficacy endpoints, to maintain the trial-wise type I error rate at 0.05, a fixed sequence multiple comparisons correction with fallback will be used. The assignment of alpha levels to hypotheses being tested will be specified in the SAP.

For endpoints that are continuous in nature number, the number of observations, mean, median, minimum and maximum, and standard deviation (SD) values will be presented as descriptive statistics. For inferential statistics:

- If the normality assumption is met, analysis of covariance (ANCOVA) using the baseline value as a covariate will be used.
- If the normality assumption is not met, a rank-ANCOVA analysis i.e., an ANCOVA analysis on rank-transformed data or other non-parametric methods will be used.
- Time to event analyses will be described with Kaplan-Meier curves and treatment groups compared with log-rank tests.

For endpoints that are categorical in nature, frequency, counts, and percentages will be presented as descriptive statistics, and a chi-square test will be used for inferential statistics.

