### Secondary Efficacy Analyses

- Percent of patients with resolution of infantile spasms at Day 14 will be compared between treatment groups.
- Percent of patients with resolution of hypsarrhythmia or a pattern of epileptic encephalopathy at Day 14 will be compared between treatment groups.
- Investigator impression of efficacy and tolerability of study drug (Clinical Global Impression – Global Improvement (CGI-I)) will be compared between treatment groups.
- Percent reduction in spasm-free days between the Initial Treatment Period (Days 1 to 14) and Screening Period (Days -14 to -1) will be compared between treatment groups.
- Percent of patients who relapse during the Extended Treatment Period will be compared between 14-day Vigabatrin + CBD responders and 14-day Vigabatrin + placebo responders. Time to relapse will be calculated and compared.
- Percent of patients with partial response at Day 14 who achieve complete response during the Extended Treatment Period will be compared. Time to complete response will be calculated and compared.

Baseline Video-EEG results (Presence of spasms, number of spasms, and presence of hypsarrhythmia, presence of epileptic encephalopathy) will be summarized by treatment group for both Awake and Sleep periods.

Historical seizure history will be recorded during the Screening Visit based on parent/caregiver recollection. Baseline percent of spasm-free days will be calculated using the seizure diary collected during the Screening Period and summarized by treatment arm.

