##### **10.6.1. Primary Efficacy Analysis**

The primary efficacy endpoint in this study is:

- Percent of patients who are considered complete responders, defined as complete resolution of spasms and hypsarrhythmia or a pattern of epileptic encephalopathy.

The percent of complete responders will be calculated for each treatment group and compared using Fisher's exact test.

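### The primary complete-response test is unadjusted although a screening video-EEG spasm count is recorded for every enrolled infant, which may give up power

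*Protocol*

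**What the plan says.** The Protocol's primary analysis (8.4.3.1) is a plain two-group comparison: complete response "will be compared between vigabatrin plus placebo and vigabatrin plus CBD 40 mg/kg/day groups using a chi square test". The SAP (10.6.1) differs in the test but is equally unadjusted: "The percent of complete responders will be calculated for each treatment group and compared using Fisher's exact test".

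A baseline measure is available. Protocol 8.4.3 states: "For each video EEG, the number of spasms will be counted and the presence of hypsarrhythmia determined". This includes the screening recording, and inclusion criterion 3 (Protocol 3.2.1) requires a screening video-EEG "including at least one cluster of electroclinical spasms", together with hypsarrhythmia. Apart from change-from-baseline summaries in Protocol 8.4.3, the count is used descriptively: "Baseline Video-EEG results (Presence of spasms, number of spasms, and presence of hypsarrhythmia, presence of epileptic encephalopathy) will be summarized by treatment group" (SAP 9.7).

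Two provisions allow some adjustment. Protocol 8.4 permits logistic regression on response as an option, with no covariates named. SAP 10.2 would add imbalanced baseline variables to a linear mixed model after the imbalance has been seen, and would stratify by developmental status if the strata turn out to differ.

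**The concern.** Randomisation makes an unadjusted test valid, but not necessarily efficient. If a baseline variable predicts the outcome, adjusting for it in a prespecified way narrows the interval around the same marginal risk difference and removes the effect of chance imbalance in that variable. Here the variable is collected anyway, and neither document gives a reason for leaving it out of the primary test.

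Power is the thing at stake, and there is little to spare: on the Protocol's own inputs the planned test falls short of the power stated.

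**Working it through.** **Inputs.** Protocol 8.2 gives "A total of 190 patients (130 and 60 patients in the two groups"), "assuming the response with vigabatrin alone is 40% and the response with vigabatrin with Cannabidiol Oral Solution is 60"%, and says that this "will provide 80% power with a two-sided alpha of 0.05 to detect a difference in response rate". Infants without a Day 14-15 video-EEG count as non-responders (Protocol 8.4.6), so no patients are lost from the primary analysis under the Protocol. The correlation rho between the screening spasm measure and response is not given anywhere. It is assumed below and varied.

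**Step 1: the plan's own figure.** For the pooled-variance two-proportion test:

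- Pooled rate = (60 × 0.40 + 130 × 0.60)/190 = 102/190 = 0.537.
- SE under the null = √[0.537 × 0.463 × (1/60 + 1/130)] = 0.0778.
- SE under the alternative = √[0.24 × (1/60 + 1/130)] = 0.0765.
- Power = Φ[(0.20 − 1.96 × 0.0778)/0.0765] = Φ(0.621) = 73.3%.

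The exact power of the Pearson chi-square test is 73.0%, and of Fisher's exact test 70.9%. The stated 80% is not reproduced; at the same allocation ratio and rates it needs 71 + 154 = 225 patients. The SAP's figure (120 and 60 patients, 62% versus 40%) does reproduce, at 80.3% by the same formula.

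**Step 2: effect of adjustment, by formula.** Adjusting for a covariate with correlation rho multiplies the variance by about (1 − rho²), so power ≈ Φ[(0.20/√(1 − rho²) − 1.96 × 0.0778)/0.0765]. For example, at rho = 0.33, 0.20/√0.891 = 0.2119, and Φ(0.776) = 78.1%.

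**Step 3: effect of adjustment, by simulation.** Logistic outcomes were simulated with one standardised baseline covariate and marginal rates held at 40% and 60%, for 60 and 130 patients. There were 5,000 trials per setting (simulation error √(0.75 × 0.25/5,000) = 0.6 points). The adjusted analysis was the risk difference standardised from a logistic model, with a degrees-of-freedom-corrected SE and a t reference.

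| Assumed rho | rho² | Adjusted, formula | Chi-square, simulated | Adjusted, simulated |
|---|---|---|---|---|
| 0 | 0 | 73.3% | 72.4% | 72.3% |
| 0.21 | 0.04 | 75.2% | 73.5% | 75.3% |
| 0.31 | 0.10 | 77.5% | 73.5% | 77.5% |
| 0.41 | 0.17 | 80.9% | 73.4% | 80.9% |
| 0.48 | 0.23 | 83.8% | 72.5% | 83.8% |

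A separate simulation with a small-sample-corrected SE gave 72.7% versus 72.6% at rho 0, 73.0% versus 78.0% at rho 0.33, and 73.4% versus 80.7% at rho 0.41.

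**Step 4: type I error.** With the correction it was 4.9-5.5%, against 4.8-5.4% for chi-square. An uncorrected large-sample z-test ran at 5.3-5.9%, so the correction is needed.

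**Step 5: what 80% would take.** Solving the formula in Step 2 for 80% power gives rho² of about 0.15, or rho of about 0.39.

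**The case against.** The case for leaving the plan alone has several parts.

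- **No loss of power is shown.** This stands. No section says that screening spasm burden predicts complete response. A reader might infer that the trial is certainly giving up power; the documents support only that it may be. Counting missing EEGs as non-response could weaken any link further.
- **The count is not the baseline value of the outcome.** This stands too. The outcome is a yes/no composite, and criterion 3 requires both spasms and hypsarrhythmia at entry, so its baseline value is the same for every correctly enrolled infant. The count is a different variable, related to one component.
- **There is no exception to explain.** A reader might see inconsistency in the baseline adjustment of the CGI-I and of spasm-free days (Protocol 8.4.3.2). But Protocol 8.4.3 goes by data type: baseline-adjusted analysis for continuous endpoints, chi-square for categorical ones. The two binary EEG secondary endpoints are unadjusted as well. The plan follows its own rule; the question is whether that rule serves the primary endpoint best.
- **The measurements are not alike.** Screening is a recording of at least 9 hours, and the outcome recording lasts 24. The Protocol has a central reader assess the screening EEG, whereas SAP 3.2.1 has the investigator read it for eligibility. So it cannot be said that baseline and outcome share method and reader throughout.
- **The gain is flattered by a liberal test.** This stands in part. Forcing the z-test to exactly 5% lowered adjusted power at rho 0.30 from 77.2% to 75.2% in one simulation. With the small-sample correction in the Working, the gain remains.
- **The plan already allows adjustment.** This does not answer the point. The logistic regression is optional and has no named covariates. The SAP's route depends on observed imbalance and uses a linear mixed model, which suits a binary endpoint poorly. Neither is a prespecified primary adjustment.

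**Conclusion.** The primary test is valid but unadjusted, and a potentially useful baseline measure goes unused in it. Compared with about 73% for chi-square, adjusted power would be about 73% at rho 0, 75% at about 0.2, 78% at about 0.33 and 81% at about 0.4. These figures rest on assumed correlations, the Protocol's rates and sample size, and a single covariate whose effect the logistic model describes adequately. The trade is favourable because almost nothing is lost if the count is uninformative. It is a matter of efficiency, not of bias.

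A reader might also infer that the lack of adjustment explains the shortfall from 80%, or that adjustment would cure it. Neither follows. The 73% comes from the sample-size inputs in Protocol 8.2 and is a separate error. Adjustment would close the gap only if rho were about 0.39 or more, which the documents give no basis to expect.

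**What to change.** In Protocol 8.4.3.1 and SAP 10.6.1, before unblinding, make the primary analysis the marginal difference in complete-response rate in the ITT population, standardised from a logistic model with two terms: treatment and log(1 + screening-EEG spasms per recorded hour). The hourly rate is needed because screening recordings have a minimum length but no fixed one. Use a small-sample-corrected robust SE or a re-randomisation p-value, and name one of them in advance. State how a missing or unreadable screening count is handled, without reference to arm, so that the ITT population stays whole.

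Report the risk difference with its 95% CI (SAP 10.6.2 currently lists only percentages and a p-value), and keep the unadjusted test as a sensitivity analysis. Carry the change into the Protocol synopsis, the general rule for categorical endpoints in Protocol 8.4.3, and the SAP's Technical Summary Report.

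Two related items need settling alongside. The Protocol and SAP must be reconciled on who reads the screening EEG, since that fixes the source of the covariate. The 80% power statement in Protocol 8.2 must be corrected in its own right.

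The cost is document wording, programming and a slightly more complex method to explain. No new data are needed and the sample size does not change. If the count proves not to be prognostic, there is no gain.

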8.4.3.2. Secondary Efficacy Analyses

- Percent of patients who relapse during the Extended Treatment Period will be compared between 14-day vigabatrin + CBD responders and 14-day vigabatrin +

placebo responders using a chi-square test. Time to relapse will be described with Kaplan-Meier curves and treatment groups compared using a log-rank test.

- Percent of patients with complete resolution of infantile spasms at Day 15 will be compared between treatment groups using a chi-square test.
- Percent of patients with complete resolution of hypsarrhythmia at Day 15 using a chi-square test.
- Investigator impression of efficacy and tolerability of study drug (Clinical Global Impression – Global Improvement [CGI-I]) will be compared between treatment groups using ANCOVA with baseline CGI-S as a covariate.
- Percent reduction in spasm-free days between the Initial Treatment Period and Screening Period will be compared between treatment groups using ANCOVA with the baseline score as a covariate.

Secondary efficacy analyses for patients with a complete response during the Initial Treatment Period who continue to the Extended Treatment Period:

- Percent of patients who relapse during the Extended Treatment Period confirmed by video EEG following parent report of relapse.
- Time to relapse.

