- For endpoints that are continuous in nature, the number of observations, mean, median, minimum and maximum, and standard deviation (SD) values will be presented as descriptive statistics. For inferential statistics, a t-test will be used to compare treatment to placebo group.
- For endpoints that are categorical in nature, frequency, counts, and percentages will be presented as descriptive statistics, and a chi-square test will be used for inferential statistics.

Primary Efficacy Analysis

- Percent of patients with complete resolution of both infantile spasms and hypsarrhythmia at Day 15 (complete response) will be compared between vigabatrin plus placebo and vigabatrin plus CBD 40 mg/kg/day groups using a chi-square test.

Secondary Efficacy Analyses

- Percent of patients who relapse during the Extended Treatment Period will be compared between 14-day complete responders receiving vigabatrin + CBD and complete responders receiving 14-day vigabatrin + placebo using chi-square test. Time to relapse will be described with Kaplan-Meier curves and treatment groups compared using a log-rank test.

- Percent of patients with complete resolution of infantile spasms at Day 15 will be compared between treatment groups using a chi-square test.
- Percent of patients with complete resolution of hypsarrhythmia at Day 15 will be compared between treatment groups using a chi-square test.
- Investigator impression of efficacy and tolerability of study drug (Clinical Global Impression – Global Improvement [CGI-I]) will be compared between treatment groups using ANCOVA with baseline CGI-S as a covariate.
- Reduction in percentage of spasm-free days between the Initial Treatment Period and Screening Period will be compared between treatment groups using ANCOVA with the Screening Period percent spasm-free days as a covariate.

Secondary Efficacy Analyses for patients with a complete response during the Initial Treatment Period who continue to the Extended Treatment Period:

- Percent of patients who relapse during the Extended Treatment Period confirmed by video-EEG following parent report of relapse.
- Time to relapse.

Safety Analyses

The Safety Population will be used for all safety assessments. All safety assessments will be descriptive and no inferential statistics are planned for safety assessments. All data listings will be provided for protocol specified safety data.

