8.1.2. Secondary Efficacy Endpoints

The secondary efficacy endpoints in the Initial Treatment Period of this study are:

- Percent of patients with resolution of infantile spasms as assessed by 24-hour video EEG from Day 14 to Day 15 (partial response).
- Percent of patients with resolution of hypsarrhythmia as assessed by 24-hour video EEG from Day 14 to Day 15 (partial response).
- Investigator impression of efficacy and tolerability of study drug (CGI-I) at Visit 6 (End of Study), or Early Withdrawal.
- Increase in the number of spasm-free days between Day 1 and Day 15 of the Initial Treatment Period, as determined by the seizure diary entries.
- For patients with a complete response during the Initial Treatment Period who continue: percent of patients who relapse during the Extended Treatment Period confirmed by video EEG following parent report of relapse, and time to relapse.

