**Criteria for evaluation:**

**Efficacy**

Primary efficacy endpoint

- Percent of patients who are considered complete responders, defined as complete resolution of spasms and hypsarrhythmia or a pattern of epileptic encephalopathy confirmed by 24-hour video-EEG from Day 13 to Day 14, as determined by the Independent Central Reader.

Secondary efficacy endpoints

- Percent of patients with resolution of infantile spasms as assessed by 24-hour video-EEG from Day 13 to Day 14 (partial response).
- Percent of patients with resolution of hypsarrhythmia or pattern of epileptic encephalopathy as assessed by 24-hour video-EEG from Day 13 to Day 14 (partial response).
- Investigator impression of efficacy and tolerability of study drug (CGI-I) at Visit 5 (End of Study) or Early Withdrawal.
- Percent reduction in spasm-free days between the Initial Treatment Period (Days 1 to 14) and Screening Period (Days -14 to -1), as determined by the seizure diary entries.
- For patients with a complete response during the Initial Treatment Period who continue: percent of patients who relapse during the Extended Treatment Period confirmed by video-EEG following parent report of relapse, and time to relapse.
- For patients with partial response during the Initial Treatment Period who continue: percent of patients who achieve complete response during the Extended Treatment Period, confirmed by video-EEG following parent report, and time to complete response.

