### **10.7. Analysis of the Secondary Efficacy Endpoints**

#### **10.7.1. Secondary Efficacy Endpoints**

The secondary efficacy endpoints in this study are:

- Percent of patients with resolution of infantile spasms as assessed by 24-hour video-EEG from Day 13 to Day 14 (partial response).
- Percent of patients with resolution of hypsarrhythmia or pattern of epileptic encephalopathy as assessed by 24-hour video-EEG from Day 13 to Day 14 (partial response).
- Investigator impression of efficacy and tolerability of study drug (CGI-I) at Visit 5 (End of Study) or Early Withdrawal.
- Percent reduction in spasm-free days between the Initial Treatment Period (Days 1 to 14) and Screening Period (Days -14 to -1), as determined by the seizure diary entries.
- For patients with a complete response during the Initial Treatment Period who continue: percent of patients who relapse during the Extended Treatment Period confirmed by video-EEG following parent report of relapse, and time to relapse.
- For patients with partial response during the Initial Treatment Period who continue: percent of patients who achieve complete response during the Extended Treatment Period, confirmed by video-EEG following parent report, and time to complete response.

Percentage of patients with partial response will be compared for each endpoint between treatment groups using Fisher's exact test.

Parent impression of efficacy and tolerability as measured by Clinical Global Impression – Global Improvement Scale (CGI-I) will be summarized by visit and status of response (complete/partial and no response). Appropriate summary statistics will be displayed and the CGI-I will also be analyzed as a continuous scale:

- 1 = Very much improved
- 2 = Much improved
- 3 = Minimally improved
- 4 = No change

5 = Minimally worse

6 = Much worse

7 = Very much worse

Percent reduction in spasm-free days, will be calculated for each treatment group. Treatment groups will be compared using ANCOVA with baseline number of spasm-free days as a covariate.

Percent of Responders who relapse and Partial Responders who achieve complete response during the Extended Treatment Period will be compared between treatment groups using Fisher's exact test. Time to relapse and time to complete response will be visualized using Kaplan-Meier curves and compared with log-rank tests.

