### **10.7.2. Presentation of the Secondary Efficacy Results**

Percentage of Partial Responders at Day 14 will be summarized by treatment group and developmental stage, and the p-value presented. CGI-I results will be summarized as a frequency table and the mean and median score with the p-value. Percent change in spasm-free days, relapse rate, and rate of partial to complete response will be summarized by treatment group and p-value. Time to relapse and time to complete response will be presented by treatment group as Kaplan-Meier curves and p-value for log-rank test.

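### The spasm-free-days secondary endpoint is defined in conflicting ways, and SAP 10.7.1 adjusts for a day count although Screening length varies

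*Protocol*

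**What the plan says.** Protocol 8.1.2, and the synopsis list of secondary endpoints, define the endpoint as "Increase in the number of spasm-free days between Day 1 and Day 15 of the Initial Treatment Period". There is no comparison with Screening.

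The synopsis analysis section instead describes "Reduction in percentage of spasm-free days between the Initial Treatment Period and Screening Period", compared "using ANCOVA with the Screening Period percent spasm-free days as a covariate".

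Protocol 8.4.3.2 has a third form, "Percent reduction in spasm-free days between the Initial Treatment Period and Screening Period will be compared between treatment groups using ANCOVA", adjusted for a baseline score that is not defined for a diary measure.

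The SAP synopsis, 9.7, 10.3.2 and 10.7.1 follow the third form: "Percent reduction in spasm-free days between the Initial Treatment Period (Days 1 to 14) and Screening Period (Days -14 to -1". SAP 10.7.1 then says: "Treatment groups will be compared using ANCOVA with baseline number of spasm-free days as a covariate". SAP 9.7, however, derives a percentage: "Baseline percent of spasm-free days will be calculated using the seizure diary collected during the Screening Period and summarized by treatment arm". SAP 10.7.2 uses a further label: "Percent change in spasm-free days, relapse rate, and rate of partial to complete response will be summarized by treatment group".

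Protocol 8.4.6 takes the percentage of spasm-free days over the diary entries made, at most 15 days per period. It and SAP 6.4.4 rule out imputation. The Screening diary covers only Visit 1 to Visit 2 (Schedule of Events, footnote l). Screening lasts up to 14 days in Protocol 3.1 and up to 14 (±5) days in SAP 3.1.

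**The concern.** A count, a difference between two percentages and a relative change are different outcomes, and no passage gives the formula for the contrast. Two programmers could analyse different variables, on different infants, with different covariates, and each could cite the documents. The endpoint is formally tested under multiplicity control (Protocol 8.4.3, SAP 10.5).

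Two consequences follow. First, a count of spasm-free Screening days has no common denominator when Screening length varies, so it is a poor covariate for an outcome built on percentages. Second, a relative change divides by the Screening value. An infant with no spasm-free Screening day has no value, and the rank-ANCOVA fallback in Protocol 8.4.3 cannot rank an undefined result. With no zero-baseline rule and no imputation, such infants leave an analysis declared to be ITT. Entry requires active spasms on video-EEG, so zero baselines are plausible.

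The word reduction also runs against the direction of benefit, but this affects only sign and label.

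**Working it through.** The documents give no power, effect size or SD for this endpoint, so there is no stated figure to reproduce.

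**1. The readings on the same infants.** Let S be Screening diary days, b the spasm-free Screening days and t the spasm-free days out of 15 on treatment. Take t = 9 (60%).

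- Point change = 100(t/15 − b/S)
- Relative reduction on counts = 100(b − t)/b
- Relative reduction on percentages = 100(b/S − t/15)/(b/S)

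| b of S | Screening percent | Point change | Relative, counts | Relative, percentages |
|---|---|---|---|---|
| 2 of 14 | 14.3 | +45.7 | −350% | −320% |
| 1 of 7 | 14.3 | +45.7 | −800% | −320% |
| 2 of 7 | 28.6 | +31.4 | −350% | −110% |
| 0 of 14 | 0 | +60.0 | undefined | undefined |

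Rows 1 and 2 have the same Screening rate but count covariates of 2 and 1. Rows 1 and 3 have the same count but different rates.

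**2. Share with a zero baseline.** The daily chance p of a spasm-free day before treatment is not in the documents, so a range is assumed. With independent days and S = 14, the share is (1 − p)^14: 0.98^14 = 0.754, 0.95^14 = 0.488, 0.90^14 = 0.229, 0.80^14 = 0.044, 0.60^14 = 0.0008. At p = 5% this is 0.488 × 190 = 93 infants. Shorter Screening raises it: at p = 5%, 70% for 7 days and 86% for 3 days. If p varies between infants as a beta with α + β = 5, the share is the product over i = 0 to 13 of (β + i)/(5 + i): 87, 70, 48 and 22% at means of 2, 5, 10 and 20%.

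**3. Power under the two readings.** Assumptions: 130 versus 60 infants; 60% versus 40% become lastingly spasm-free from a day uniform on 4 to 14; all other days are spasm-free with chance p; 15 treatment days and 14 Screening days. Ranked change is regressed on arm and ranked Screening value, two-sided 0.05, with 4000 runs per case (Monte Carlo SE at most 0.8 points).

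| p | Point change, all infants | Relative change, b > 0 only | Point change, b > 0 only |
|---|---|---|---|
| 2% | 61.4 | 19.2 | 19.3 |
| 5% | 61.4 | 35.8 | 35.6 |
| 10% | 57.5 | 46.0 | 46.3 |
| 20% | 53.5 | 49.6 | 52.1 |
| 40% | 43.4 | 40.8 | 43.3 |

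The last two columns are close, so the loss comes mainly from excluding infants and not from the relative scale. With 40% in both arms, rejection is 4.2 to 5.6%.

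**4. Number versus percent as covariate.** Same model, point change, all infants, Screening length assumed uniform on 1 to 14 days.

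| p | Percent covariate | Number covariate |
|---|---|---|
| 2% | 61.1 | 61.2 |
| 5% | 59.4 | 59.1 |
| 10% | 56.2 | 54.5 |
| 20% | 51.5 | 44.2 |
| 40% | 40.1 | 25.2 |

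Null rejection is 4.2 to 5.4%. Linear ANCOVA, the first choice in Protocol 8.4.3, loses more (2000 runs): 56% with percent against 50% with number at p = 10%, and 51% against 39% at p = 20%. A separate linear simulation with baseline chances varying between infants gave the same mean treatment estimate (9.6 points) with either covariate, and standard errors of 3.36 (percent) and 3.68 (number): 3.68/3.36 = 1.10, or about 9% larger before rounding.

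**The case against.** A usable definition can be assembled from the documents. Protocol 8.4.6 defines the percentage, the synopsis names the contrast and the Screening-percent covariate, and SAP 9.7 derives the same baseline percentage. Under that reading no infant is lost to a zero baseline. This stands, and it makes the zero-baseline harm conditional. It does not settle the matter, because 8.4.6 defines the percentage and not the contrast, and Protocol 8.1.2, 8.4.3.2 and SAP 10.7.1 say something else.

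The SAP rests on protocol V2.0 of 30 October 2017 and says it may be updated. That explains its Days 1 to 14, and the covariate could be corrected in the same update. It does not explain three forms within the current protocol.

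The covariate loss depends on analysing a change score. With the treatment-period percentage as outcome, number and percent covariates give equal power at p = 40%: 44.2 and 44.2% (linear), 45.5 and 45.6% (rank). Also, in linear ANCOVA adjusted for Screening percent, change and treatment-period percentage give the same test. With complete 15-day diaries and that covariate, a count of spasm-free treatment days would therefore agree with the percentage-point reading. Both points stand, but the plan describes a change and SAP 10.7.1 names the count.

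Finally, ranking the treatment-period percentage gave somewhat more power than ranking the change (45.6 against 40.2% at p = 40%, 53.2 against 49.8% at 20%). The choice of ranked outcome is partly preference; that one must be named is not.

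**Conclusion.** The concern holds and should be fixed. The conflict in definition and covariate is textual and needs no assumption.

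The size of the consequences does rest on assumptions: the daily chance of a spasm-free day, the distribution of Screening lengths and the response model. Under them, the relative reading costs about 42 points of power at p = 2% (61.4 − 19.2) and about 3 at 40% (43.4 − 40.8). The day-count covariate runs the other way, from nothing at 2% to about 15 points at 40% (40.1 − 25.2).

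The harm is lost precision and, under the relative reading, loss of the ITT set. Exclusion depends only on a pre-treatment value, so type I error is not inflated. The primary endpoint is not affected. SAP section 1 requires analysis decisions before database lock, so this is a matter of writing down one definition and not a charge of choosing it after unblinding.

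**What to change.** In both documents:

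- Define one variable: percent of diary days spasm-free in the Initial Treatment Period minus percent of diary days spasm-free in Screening, in percentage points, positive meaning improvement.
- State one day range, aligned with the current protocol schedule.
- Use Screening percent spasm-free days as the ANCOVA covariate, replacing the day count in SAP 10.7.1 and the undefined baseline score in Protocol 8.4.3.2 and the SAP synopsis.
- Name this change score as the outcome to be ranked if rank-ANCOVA is used.
- Use the same label in the endpoint lists, hypotheses, analysis sections and SAP 10.7.2.

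An infant with no Screening diary entry remains missing under the no-imputation rule; this change does not alter that. The cost is wording only. No new data are needed, since both percentages are already planned in Protocol 8.4.6 and SAP 9.7.
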